# **Background:**

Over 80% of critically ill patients receive antibiotic treatment over their ICU stay and it is well documented that it leads in a reduction of the diversity of colonic bacterial flora. In turn, this leads to overgrowth of pathogenic species incl. Clostridium difficile (C.dif.) and multi-drug resistant Enterobacteriaceae and Enterococci. Restoration of physiological bacterial flora is prolonged and a significant proportion of patients suffer from postantibiotic diarrhoea. In particular, postantibiotic diarhea in the critically ill that is associated with C. dif. infection may lead to prolonged ICU stay or complications such as toxic megacolon, sepsis and death. Even non-clostridial postantibiotic diarhoea represent a significant burden to ICU patients and staff, impairing patients dignity and comfort and often increasing their length of stay. Current treatment options are limited as neither prebiotic nor probiotic were found to be consistently efficient in the critically ill and have been found risky in some settings, e.g. pancreatitis. Changes of colonic microbiome are well documented in the critically ill and length and mechanisms of restoration of colonic microbiome are yet unknown. It is also unknown to what extent changes in colonic flora contribute to nosocomial infections by MDR Gram negatives in the critically ill.

In the light of this, restoring physiological bacterial flora in the colon by faecal bacteriotherapy (FBT) could potentially be beneficial. FBT has been shown to be safe and effective not only in the prophylaxis of recurrence after the antibiotic treatment, but also as the first-line treatment in the population of non-critically ill patients with C. dif. infections .

The study will be performed in accordance with the protocol, The Declaration of Helsinki and principles of Good Clinical Practice: Consolidated Guidelines. The protocol is consistent with any applicable local regulations.

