# Secondary end-points are:

- Composite number of adverse events such as new-onset sepsis, toxic megacolon, positive post FBT blood culture, or other SAE assessed by the physician-in-charge as possibly related to FBT.
- SOFA score at days 4 and 7.
- Percentage of patients that are recurrence-free at time of hospital discharge or day 28, whichever occur earlier.
- Subgroup analysis will be performed for patients who are C. dif. positive vs. negative and those who will receive antibiotics for a new extraabdominal infection vs. those who do not.

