## Method:

*Design*: prospective, randomised, controlled, parallel group, open-label, assessor blinded feasibility trial.

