## Study subjects:

- Inclusion Criteria: All of the following: Informed consent (see below), Age > 18 yrs., In-patient in ICU or HDU (incl. burn unit) and expected to stay for >7 days, Diarrhoea following antibiotic treatment defined as 3 or more stools per day or Bristol type 7 stool in the volume >300 ml/day if stool derivative device is in place, persisting for 24 hours despite enteral feeding formula has been stopped.
- Exclusion criteria: Death appears imminent or ceilings of care put in place, presence of new-onset sepsis defined as per 2016 definition, lactate >2.0 mM, colon diameter > 9 cm on plain AXR, the necessity of ongoing antibiotic treatment for another reasons. Unable to tolerate enema for any reason (e.g. surgery of the GI tract in the past year). Pregnant and lactating woman. Patients with a history of severe anaphylactic food allergy, any other reason

22.9.2021 Protocol version 9.2

which — as per judgement of the treating clinician — makes faecal transplantation unsafe or not feasible (Note: All screening failures based on this criterion will be reported separately, inc. the reason why it was considered unsafe or not feasible to proceed).

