#### Procedures at baseline:

#### Day 0

In patients with diarhea, after confirmation of negative pregnancy test in fertile women informed consent will be subscribed. The drug chart will be reviewed and all medication that can be contributing to diarhea will be stopped if it is considered safe to do so. Abdominal X ray will be performed to rule out pneumoperitoneum or megacolon. After obtaining baseline stool sample (sent for study analyses but also for GDH, C. dif. toxins A and B and faecal calprotectin), blood sample will be tested for standard tests ( biochemistry, blood count, etc.). Stool and plasma samples will be frozen at -80 C for later analysis.

Randomisation will be performed by sealed envelope in the evening of day No.0. Enteral nutrition will be stopped at 18:00 at the latest.

### Day 1

The patient will be physically examined in the morning, including the determination of the degree of SOFA score (a set of laboratory results and examinations estimating organ function). Stool and plasma samples will be frozen at -80 C for later analysis. The frequency, amount and structure of the patient's stools will be recorded. Patients will be treated for their primary disease throughout the study according to established standard procedures.

In both groups adequate hydratation will be taken care of by replacing the fluids lost by diarrhea with infusion. Throughout the treatment, we monitor the patient's vital functions (body temperature, heart rate, blood pressure, blood oxygen saturation)

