# Monitoring of safety:

Although it is potentially beneficial and has been safely performed in ICU patients, there are only limited data about FBT safety in patients with potentially disrupted intestinal barrier. In turn, following measures have been taken to maximise safety of the current study for patients:

- Treating clinician will not be blinded to treatment allocation and they will be encouraged to speak up should any safety concerns arise.
- Before and 3 hours after FMT, vital signs, blood cultures, endotoxin and early cytokine levels will be measures to specifically look at potential bacterial translocation.
- All patients' vital functions will be continually monitored as per local standards. Frequency, volume and character (as per Bristol scale) of stools will be recorded in 12 hour intervals.
- Onset of sepsis or elevation lactate > 2mM or the presence of pyrexia >38 C with >30% rise of inflammatory markers without clear alternative reason (e.g. HAP) will trigger, in both groups, the addition of intravenous tigecycline or intravenous vancomycine, if C. dif positivity is known or suspected.
- I.v. antibiotics efficient against C. dif. can be added in both groups if a treating clinician considers this appropriate. Reason for doing so will be recorded.
- Should a SUSAR appear, it will be reported as per local legislature and within 48 hours reviewed by the team of investigators, together with independent safety advisors (prof. [name]. Dept. of Infectious Diseases, Na Bulovce Hospital, Prague and Dr.[name], REB Chair FNKV Univ. Hospital), a representative of nursing staff independent on the study. Two SUSARs in the intervention group would automatically lead to termination of the trial for safety reasons.

Unique Protocol ID: 2021-002290-25 22.9.2021 Protocol version 9.2

In addition, the same team will meet ad hoc whenever safety concerns arise. The
team will review data collected from first 8 subjects who have been randomised and
focus on the analysis of adverse events. In particular, the team will review the dynamics of body temperature, heart rate, blood pressure, lactate and blood cultures
before and after FMT. The decision will be taken to continue or terminate the study.

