# Statistical plan:

Safety parameters will be reported on intention-to-treat basis. Primary outcome will be compared by as unadjusted hazard ratio of not being cured (with 95% interval) in a per protocol analysis. The subset of patients with C. dif positivity will be analysed separately.

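### The planned antibiotic subgroup is defined by an event after randomisation, so an FBT-versus-control comparison within it can mislead if allocation influences who receives antibiotics

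*Combined protocol and SAP*

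**What the plan says.** The last item under Secondary end-points announces subgroup analyses by two variables. One is C. dif. status. The other is "those who will receive antibiotics for a new extraabdominal infection vs. those who do not".

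The following places bear on the second variable:

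- Study subjects lists among the exclusions "the necessity of ongoing antibiotic treatment for another reasons".
- Procedures at baseline, Day 0: "Randomisation will be performed by sealed envelope in the evening of day No.0". The stool sample for C. dif. testing is also taken on that day.
- Method describes a "prospective, randomised, controlled, parallel group, open-label, assessor blinded feasibility trial".
- Monitoring of safety: "Treating clinician will not be blinded to treatment allocation and they will be encouraged to speak up should any safety concerns arise". The same section adds that "I.v. antibiotics efficient against C. dif. can be added in both groups if a treating clinician considers this appropriate".
- Background: "It is also unknown to what extent changes in colonic flora contribute to nosocomial infections by MDR Gram negatives in the critically ill".
- Statistical plan, the only subgroup named: "The subset of patients with C. dif positivity will be analysed separately".

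No section gives an outcome, a time window, a contrast or a method for the antibiotic subgroup, or a caution on how to read it.

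**The concern.** A subgroup comparison keeps the protection of randomisation when membership is fixed before allocation. C. dif. status meets that test, because it comes from the day 0 stool sample. The antibiotic variable does not. Patients with a continuing need for antibiotics are kept out, so antibiotics for a new infection must start later, after allocation is known to the treating team.

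The protocol leaves two routes open by which allocation could alter membership. First, unblinded clinicians may have a different threshold for diagnosing and treating a suspected infection in a patient who has received FBT. Second, FBT may change the risk of infection itself, which the Background treats as an open question.

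If either route operates, and sicker patients are more likely both to receive antibiotics and to have diarrhoea on day 7, the FBT and control patients inside a subgroup differ in severity. A difference could then appear with no effect of FBT on diarrhoea. New antibiotics may also cause diarrhoea, which is the premise of the trial. In that case the subgroup is also split on a step between allocation and outcome, and the contrast inside it no longer measures the whole effect of FBT.

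At stake is a secondary result that would be reported beside the C. dif. subgroup as if the two had equal standing.

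**Working it through.** **Arm size.** The plan's figure (Sample study size) is 36 patients, from success of 45% and 66%, a margin of 20 points, one-sided 5% and 80% power:

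n per arm = [0.45×0.55 + 0.66×0.34] × (1.645 + 0.842)² / (0.21 + 0.20)² = 0.4719 × 6.18 / 0.1681 = 17.4, rounded up to 18, so 36 in total.

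The figure reproduces. It matters here only because it fixes 18 patients per arm.

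**Assumed inputs.** The documents give no rate of new antibiotics, no prognostic strength and no effect of arm on prescribing. I assume half the patients are severe, with day-7 failure of 75% if severe and 35% if not, identical in both arms. Overall failure is 0.5×0.75 + 0.5×0.35 = 55%, which matches the plan's 45% control success. The true effect of FBT on diarrhoea is therefore zero, overall and at each level of severity.

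**Formula.** With antibiotic rates a₁ (severe) and a₀ (not severe) in an arm:

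- severe share with antibiotics: s = 0.5a₁ / (0.5a₁ + 0.5a₀)
- severe share without antibiotics: the same, with 1−a₁ and 1−a₀
- failure in the subgroup = 0.35 + 0.40s
- spurious difference = 0.40 × (s in FBT − s in control)

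**Worked case (c).** Control has rates 50% and 10%, so s = 0.25/0.30 = 0.833 and failure is 68.3%. FBT has rates 50% and 40%, so s = 0.25/0.45 = 0.556 and failure is 57.2%. The difference is −11.1 points. Without antibiotics, s = 0.25/0.70 = 0.357 (49.3%) in control and 0.25/0.55 = 0.455 (53.2%) in FBT, a difference of +3.9 points.

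| Case | Control a₁ / a₀ | FBT a₁ / a₀ | Spurious difference in failure, with antibiotics | Without |
|---|---|---|---|---|
| (a) allocation has no influence | 50% / 20% | 50% / 20% | 0 | 0 |
| (b) fewer antibiotics in non-severe | 50% / 30% | 50% / 10% | +8.3 | −2.4 |
| (c) more antibiotics in non-severe | 50% / 10% | 50% / 40% | −11.1 | +3.9 |
| (d) more antibiotics in severe | 30% / 20% | 70% / 20% | +7.1 | −7.8 |

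Swapping the arm labels reverses each sign, so both directions are possible. With a stronger prognostic difference (failure 90% and 20%, multiplier 0.70), (b) becomes +14.6 and −4.2, and (c) becomes −19.4 and +6.8.

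These cases are illustrations, not bounds. At the original prognosis, a larger shift in non-severe patients (40% to 5%, with severe at 60% in both arms) gives +12.9 and −4.1.

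**Precision.** The approximate 95% half-width for a difference, at 50% failure and m patients per arm, is 1.96 × √(2×0.25/m).

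| Share with new antibiotics, both arms | m with antibiotics | Half-width | m without | Half-width |
|---|---|---|---|---|
| 20% | 3.6 | 73 points | 14.4 | 37 points |
| 30% | 5.4 | 60 points | 12.6 | 39 points |
| 50% | 9.0 | 46 points | 9.0 | 46 points |

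Where the shares differ by arm, so do the cells. In case (c), 30% and 45% of 18 give 5.4 control and 8.1 FBT patients with antibiotics, and a half-width of 1.96 × √(0.25/5.4 + 0.25/8.1) = 54 points. The normal approximation is rough at these sizes.

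**The case against.** The strongest reply is that nothing in the documents shows that FBT changes new infection or prescribing. That stands. A reader might infer that the comparison is certain to be biased, but case (a) gives exactly zero, and the Background calls the link between flora and nosocomial infection unknown. The bias is conditional.

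A reader might also point to the monitoring for translocation and new-onset sepsis as evidence that FBT affects membership. This fits poorly. The subgroup is limited to extra-abdominal infection, perhaps in order to select infections unrelated to the bowel. The allowance for added i.v. antibiotics in Monitoring of safety concerns drugs active against C. dif. It shows that unblinded clinicians have discretion, but those are not the antibiotics that define the subgroup. Unblinded prescribing and the open question in the Background are the better grounds.

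Third, the plan does not state that arms will be compared within the subgroup. True: outcome, window and contrast are all absent. A between-arm contrast is the natural reading of a subgroup analysis listed under secondary end-points, and nothing labels it descriptive, but it remains a reading.

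Finally, this is a 36-patient feasibility trial in which noise would swamp the bias. That limits the harm. It is also a reason not to draw a between-arm inference from so few patients.

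**Conclusion.** The point holds in conditional form. The variable is a post-randomisation event that no other section handles. An FBT-versus-control contrast within it is unprotected if allocation changes who receives antibiotics and antibiotic use is linked to diarrhoea. An open-label design does not allow that influence to be ruled out in advance. Similar antibiotic totals by arm would not settle it either, since the mix of patients could still differ.

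The size rests wholly on assumed inputs: 0 to about 11 points in the main cases and about 19 with strong prognosis. Random error in the antibiotic subgroup, at roughly 46–73 points, would usually be larger. No particular false message can be predicted. A reader might expect FBT to look ineffective among patients given antibiotics, but case (c) gives the reverse and case (b) the opposite sign again.

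The primary analysis, the sample size and the C. dif. subgroup are unaffected. This is a minor to moderate point.

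**What to change.** In Secondary end-points, take one of two courses:

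- remove antibiotic use as a treatment-effect subgroup; or
- keep it, labelled as descriptive and non-causal, with no between-arm estimate, test or interpretation, and with a stated window that ends at the outcome assessment. Without a window, antibiotics started after day 7 could classify a patient for a day-7 outcome.

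In either case, report new antibiotic use by arm as an outcome in its own right, with numbers, timing and reasons. Keep baseline C. dif. status as the pre-specified subgroup, which brings this section into line with the Statistical plan.

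The cost is wording. Concomitant medication is already recorded in the first week, and Assessment of primary outcome provides for antibiotic monitoring afterwards. The one possible addition is a field for the indication of each new antibiotic, because recording of the reason is stated only for added i.v. antibiotics active against C. dif. The sample size stays at 36, and no treatment rule changes.

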# Exploratory outcomes:

- Diversity, density and composition of faecal microbiome by quantitative sequence-based mapping
- Changes in bowel metabolom incl. bile acid spectrum as assessed by NMR and GS/MS
- Bowel barrier integrity and inflammation assessed by plasma markers (citrulline, endotoxin, D-lactate, IL-6, IL-8, IL-12, TNF-a, LL-37 cathelidicine), faecal markers (calprotectine)
- Donor's diversity and viability of faecal microbiome by quantitative sekvence-based mapping and cultivation

## Method:

*Design*: prospective, randomised, controlled, parallel group, open-label, assessor blinded feasibility trial.

## Study subjects:

- Inclusion Criteria: All of the following: Informed consent (see below), Age > 18 yrs., In-patient in ICU or HDU (incl. burn unit) and expected to stay for >7 days, Diarrhoea following antibiotic treatment defined as 3 or more stools per day or Bristol type 7 stool in the volume >300 ml/day if stool derivative device is in place, persisting for 24 hours despite enteral feeding formula has been stopped.
- Exclusion criteria: Death appears imminent or ceilings of care put in place, presence of new-onset sepsis defined as per 2016 definition, lactate >2.0 mM, colon diameter > 9 cm on plain AXR, the necessity of ongoing antibiotic treatment for another reasons. Unable to tolerate enema for any reason (e.g. surgery of the GI tract in the past year). Pregnant and lactating woman. Patients with a history of severe anaphylactic food allergy, any other reason

22.9.2021 Protocol version 9.2

which — as per judgement of the treating clinician — makes faecal transplantation unsafe or not feasible (Note: All screening failures based on this criterion will be reported separately, inc. the reason why it was considered unsafe or not feasible to proceed).

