## Hypothesis and aims:

We hypothesise that FBT will be feasible as first-line treatment of postantibiotic diarrhoea in the critically ill, incl. those with uncomplicated C. dif. infection.

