# Primary end-point:

• Percentage of patients with treatment failure at day 7 after randomisation. Treatment failure is defined as either failure to administer allocated treatment for any reason or the presence of diarrhoea on day 7 after randomisation (as assessed by personnel blinded to treatment allocation).

22.9.2021 Protocol version 9.2

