#### Sample study size:

We plan to randomise 36 patients in 1:1 ratio: This is a pilot trial, with primary outcome being feasibility and safety of faecal bacterial transplantation in the population of critically ill adults with C. dif. positivity and diarrhoea. However, with 36 randomised patients, the study will have sufficient power to determine non-inferiority against standard-of-care based on data available in FBT in patients with C. dif. In two trials in non-critically ill patients, the success of FBT was 69% (22 out of 32) or 56% (5 out of 9) as compared to 45% cured by oral metronidazole. Assuming that clinically significant difference between the two methods is 20% and the intervention will be as effective in ICU patients as it was in the non-critically ill group (curing 27 out of 41, ie. 66%), if there is a true difference in favour of the experimental treatment of 21%, then 36 patients are required to be 80% sure that the upper limit of a one-sided 95% confidence interval (or equivalently a 90% two-sided confidence interval) will exclude a difference in favour of the standard group of more than 20%. The expected duration of participation in the study is 6 months.

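### Feasibility is the trial's stated question, but delivery of FBT is seen only inside a composite with day-7 diarrhoea, and only in patients already screened for it

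*Combined protocol and SAP*

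**What the plan says.** Three places make feasibility the question. Hypothesis and aims: "We hypothesise that FBT will be feasible as first-line treatment of postantibiotic diarrhoea in the critically ill". Method: "prospective, randomised, controlled, parallel group, open-label, assessor blinded feasibility trial". Sample study size: "This is a pilot trial, with primary outcome being feasibility and safety of faecal bacterial transplantation".

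The Primary end-point section defines treatment failure as "failure to administer allocated treatment for any reason or the presence of diarrhoea on day 7 after randomisation". The Secondary end-points and Exploratory outcomes sections list no outcome for delivery, retention or screening yield, and no section gives a numerical criterion for feasibility.

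The Statistical plan compares the primary outcome as an "unadjusted hazard ratio of not being cured (with 95% interval) in a per protocol analysis". The per-protocol set is not defined. The only stated rule is under Informed consent procedure: data of patients who refuse consent are left out of it.

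The exclusion criteria under Study subjects act before randomisation. One is "Unable to tolerate enema for any reason (e.g. surgery of the GI tract in the past year". Another is any other reason that, in the treating clinician's judgement, "makes faecal transplantation unsafe or not feasible". A note attached to the second reads: "All screening failures based on this criterion will be reported separately, inc. the reason why it was considered unsafe or not feasible".

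**The concern.** A trial that sets out to show that FBT is feasible needs an estimate of how often FBT could be given. Here that quantity has no line of its own. It is joined by an *or* to a measure of efficacy, and the result is to be analysed in a set that may leave out the patients in whom delivery failed. The report could then call FBT feasible without any pre-specified figure behind the word.

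There is also a question of whom the figure describes. FBT is given by retention enema (Intervention group), so inability to tolerate an enema is a central way for delivery to fail. Those patients, and those for whom a clinician thinks FBT cannot be done, never reach randomisation. Delivery among randomised patients is therefore delivery in people already judged able to have it, whereas the hypothesis speaks of the critically ill in general.

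**Working it through.** **Inputs.** From Sample study size: 36 patients randomised 1:1, control success 45%, FBT success 27/41 = 66%, margin 20 points, one-sided 5%, 80% power. The documents give no delivery rate and no screening yield, so every value used for these below is an assumption.

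**1. The plan's own figure.** With unpooled variance, n per arm = (1.645 + 0.842)² × (0.45×0.55 + 0.66×0.34) / (0.21 + 0.20)² = 6.18 × 0.4719 / 0.1681 = 17.4, rounded up to 18, or 36 in total. This agrees with the protocol. It is sized for the comparison of success, not for the precision of a delivery proportion.

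**2. What the composite can show.** Let d be the proportion delivered and c the proportion free of diarrhoea on day 7 among those delivered. Failure among all randomised = 1 − d×c.
- d = 1, c = 0.60: failure = 0.40.
- d = 2/3, c = 0.90: failure = 0.40.

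At the protocol's own 66% success the same holds. In the table c = 0.66/d, and the last column is 1 − c, which is what an analysis of delivered patients only would show.

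| d | c | Failure, all randomised | Failure, delivered only |
|---|---|---|---|
| 100% | 66% | 34% | 34% |
| 90% | 73.3% | 34% | 26.7% |
| 80% | 82.5% | 34% | 17.5% |
| 70% | 94.3% | 34% | 5.7% |

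Neither a 34% nor a 40% failure rate tells the reader what d was. The comparison between arms does not help. For C. dif.-negative controls the allocated management is to wait for spontaneous resolution (Control group), which can hardly fail to be delivered.

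**3. What the per-protocol set could do.** Suppose the set drops undelivered patients and c is fixed at 66%. Failure then reads 34% whatever d is. In all randomised patients it would be 1 − 0.66d: 40.6% at d = 90%, 47.2% at 80% and 53.8% at 70%. The delivery signal would be gone even from the composite.

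**4. Precision of delivery as its own outcome.** Exact (Clopper-Pearson) 95% intervals with 18 patients in the FBT arm:
- 18/18: 81.5% to 100%
- 17/18: 72.7% to 99.9%
- 16/18: 65.3% to 98.6%
- 15/18: 58.6% to 96.4%

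**5. Effect of the exclusions (illustration).** Let e be the number of otherwise eligible patients excluded for enema intolerance or as not feasible, each taken as not deliverable. Delivery among all otherwise eligible patients = 36/(36 + e) × d. With an assumed d = 16/18 = 88.9%:
- e = 4: 0.900 × 0.889 = 80.0%
- e = 9: 0.800 × 0.889 = 71.1%
- e = 12: 0.750 × 0.889 = 66.7%
- e = 18: 0.667 × 0.889 = 59.3%

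The last line needs one such exclusion for every two patients randomised.

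**The case against.** A reader might infer that the trial must return too favourable an answer on feasibility. The documents do not support that, for four reasons.

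- **The screening note.** The protocol promises the clinician-judged exclusions with reasons, so a reader can put those patients back into the denominator. This stands for that group. The note is a reporting promise, however, and is not tied to any outcome or conclusion.
- **Ordinary safety restrictions.** The clinician item joins unsafe with not feasible, and the example for enema intolerance is recent gastrointestinal surgery. Delivery among eligible patients is not biased for eligible patients. It simply does not extend to everyone in the ICU with diarrhoea. This stands, and it makes the matter one of target population.
- **Direction of the composite.** Counting non-delivery as failure works against FBT. Merging hides delivery; it does not inflate it.
- **Recoverable data.** Direct access to source data/documents requires the whole FBT procedure to be recorded, and Assessment of primary outcome records diarrhoea as its own item. The two components can be separated later. This also stands, but nothing commits the sponsor to separating them.

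A reader might also infer that enema-intolerant patients will not be counted at all. That would be an inference from silence. The clinician item continues the list of reasons before it, so the reach of the note's reference to this criterion is ambiguous. All that can be said is that it is unclear whether enema intolerance is covered.

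Finally, an estimate of delivery without a stated criterion still does not test the hypothesis. That is true. With 18 patients the intervals in step 4 are wide, and the word feasible will remain a judgement unless the sponsor says beforehand what would count.

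**Conclusion.** The concern holds in this form. Feasibility is the central question, yet the only randomised measure of delivery is a composite from which delivery cannot be read, and an undefined per-protocol set may remove the undelivered patients altogether. The first part is a matter of definition and needs no assumed figures. The second depends on how the set is drawn: the 34% against 41% to 54% contrast assumes that undelivered patients are dropped and that cure given delivery is 66%.

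The exclusions narrow the population to which any delivery figure applies. How much this matters cannot be known from the documents; the 80% to 59% range rests wholly on assumed counts. It does not show that the trial's answer will be too favourable, and the screening note already covers part of the gap.

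The sample size, eligibility and treatment are unaffected. This is a change to outcomes, analysis set and reporting that should be made before the data are analysed.

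**What to change.** 1. Keep the composite primary endpoint and analyse it in all randomised patients. Any per-protocol analysis should be supportive, with its set defined and the number of consent refusals reported.
2. Name a separate feasibility outcome: the proportion of all patients randomised to FBT who received the allocated FBT, with an exact 95% interval. State in advance what counts as received, since the Intervention group section has FBT repeated in C. dif.-positive patients.
3. Report diarrhoea on day 7 as its own line beside the composite.
4. Extend the screening-failure note to enema intolerance. Report the number excluded on each ground, with unsafe separated from not feasible, next to the delivery proportion.
5. Limit the conclusion on feasibility to patients who pass these exclusions. Show the proportion among all otherwise eligible patients (step 5) as a supporting figure only. It has no interval as written, and its target population is open to debate.

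The cost is one more reason code in the screening log and a few lines in the results. The supporting figure also needs the remaining criteria checked in patients already excluded, which is some added screening work. The feasibility statement will be narrower or less favourable than it would otherwise be.
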